1.4.1 Rationale for correlative study

Initially, our study selected only KRAS wild-type tumors for exon 2 (codon 12 and 13) but not for the additional RAS mutations [KRAS exon 3 (codon 61) and exon 4 (codons 117 and 146) and NRAS exon 2 (codons 12 and 13), exon 3 (codon 61), and exon 4 (codons 117 and 146)]. Thus, we proposed to collect patient tumor samples so that we could retrospectively analyze them for the additional RAS mutations to see if progression-free survival and overall survival are impacted by additional mutations. If patient tumors are analyzed for the additional RAS mutations prior to enrollment, then tissue collection is not necessary.

2. STUDY OBJECTIVES

2.1. Primary Objective

The primary objective for this phase II trial is to determine the median progression-free survival in patients treated with FOLFIRI and panitumumab who have RAS wild-type , metastatic colorectal carcinoma and have already progressed on FOLFIRI + Bevacizumab.

2.2 Secondary Objectives

- To determine the frequency and severity of toxicities of the regimens.
- To determine overall response rate
- To determine the median overall survival and the overall survival rate at 1 year

3. STUDY DESIGN

3.1. Study design

This is an open-label, prospective phase II clinical trial, with a primary endpoint of progression-free survival (PFS). Patients must fail a combination of FOLFIRI and bevacizumab prior to being considered for this study. At the time of consideration, all participants will be screened for RAS mutations and only patients who are considered RAS-wild type [KRAS exon 2 (codon 12 and 13), KRAS exon 3 (codon 61) and exon 4 (codons 117 and 146) and NRAS exon 2 (codons 12 and 13), exon 3 (codon 61), and exon 4 (codons 117 and 146)] will be enrolled on the study. Patients eligible for this study will receive a modified regimen of FOLFIRI as outlined in this study along with panitumumab as outlined in section 6.2. Each cycle will consist of days 1 and 15 as outlined in section 6.2. Patients will be restaged after 2 cycles of therapy. If there is no evidence of progressive disease, patient will continue on study. They will be monitored at regular intervals with serial laboratory testing as well as periodic scans to assess response to treatment as outlined in section 5.5.

3.2 Sample Size and Accrual Rate:

A total of 25 patients will be required to test the null hypothesis that there is no difference in median PFS between the study regimen and the historical control. Please refer to Section 9 for details regarding the statistical methods. We anticipate a uniform accrual rate of 2 patients with KRAS wild type mCRC per month from the 2 participating institutions (The Ohio State University (lead)), no lost to follow-up, and an additional 6 months of planned follow-up after accrual is completed.

4. SELECTION CRITERIA

4.1. Inclusion Criteria

To be eligible for inclusion, each patient must fulfill each of the following criteria:

1. Patients with advanced adenocarcinoma of the colon or rectum not curable with surgery or radiotherapy and have been previously treated for their disease with FOLFIRI plus bevacizumab in the **first line** metastatic setting. Patients will only be eligible if their last line of therapy prior to enrolling onto the study was FOLFIRI and bevacizumab received **no more than 6 months prior** to enrolling in this study. They should have been treated with FOLFIRI plus bevacizumab until disease progression is radiographically documented
2. Patients' tumors will need to be tested for the *RAS* mutation status. Only those patients with wild-type or unmutated *RAS* oncogene are eligible to participate in this study.
3. Provide written informed consent prior to study-specific screening procedures, with the understanding that the patient has the right to withdraw from the study at any time, without prejudice.
4. Prior cetuximab is allowed in the **adjuvant but not in the metastatic setting**, but must have been **completed at least 6 months** before enrolling on this trial.
5. Age \geq 18 years
6. ECOG performance status \leq 1
7. Life expectancy greater than 12 weeks

8. No active brain metastasis. Previously surgically treated or irradiated lesions are allowed if not clinically active.
9. Has a negative serum pregnancy test within 7 days of first dose of study treatment (female patients of childbearing potential).
10. Ability to understand and willingness to sign a written informed consent
11. No history of severe reactions to 5-FU, irinotecan, or a monoclonal antibody
12. Adequate organ and marrow function as defined below:

Leukocytes	$\geq 3000/\mu\text{L}$
Absolute neutrophil count	$\geq 1500/\mu\text{L}$
Platelets	$\geq 100,000/\mu\text{L}$
Hemoglobin	$\geq 9\text{ mg/dL}$
Total Bilirubin	$\leq 1.5 \times \text{ULN}$
AST/ALT	$\leq 3 \times \text{ULN}$ (or $< 5 \times \text{ULN}$ with liver metastases).
Creatinine Clearance	(CrCl) $\geq 30 \text{ ml/min}$ (Cockcroft-Gault Equation)
Magnesium	\geq lower limit of normal
13. Measurable disease is required according to RECIST 1.1 criteria (45).
14. The effects of Panitumumab on the developing human fetus are unknown. For this reason and because monoclonal antibodies as well as other therapeutic agents used in this trial are known to be teratogenic, women of child-bearing potential and men must agree to use adequate contraception (hormonal or barrier method of birth control; abstinence) prior to study entry and for the duration of study participation and up to 6 months after completing therapy. Should a woman become pregnant or suspect she is pregnant while participating in this study, she should inform her treating physician immediately.

4.2. Exclusion Criteria

Patients who fulfill any of the following criteria will be excluded:

1. Pregnant or breast-feeding women. Women of childbearing potential with either a positive or no pregnancy test at baseline. Woman or men of childbearing potential not using a reliable and appropriate contraceptive method. (Postmenopausal woman must have been amenorrheic for at least 12 months to be considered of non-childbearing potential).
2. Sexually active males unwilling to practice contraception during the study and 6 months beyond.
3. History of interstitial lung disease (eg, pneumonitis or pulmonary fibrosis) or evidence of interstitial lung disease on baseline chest CT scan.
4. KRAS or NRAS mutant tumors.
5. Active inflammatory bowel disease or other bowel disease causing chronic diarrhea (defined as \geq CTC grade 2 (CTCAE version 4.0))
6. Clinically significant cardiovascular disease that is not well-controlled with medication (including myocardial infarction, unstable angina, symptomatic congestive heart failure, serious uncontrolled cardiac arrhythmia) or myocardial infarction within ≤ 1 year or serious concurrent infection.
7. Bevacizumab within the last 3 weeks before enrollment on trial
8. Patient is more than 6 months since the last dose of FOLFIRI.
9. Patients who have required toxicity related dose reductions of greater than 50% of the original dose of infusional 5-FU and/or irinotecan during the administration of FOLFIRI/bevacizumab .

10. Prior exposure to panitumumab in any setting
11. Prior exposure to cetuximab in the metastatic (Stage IV) setting.
12. Radiotherapy \leq 14 days prior to enrollment. Patients must have recovered from all radiotherapy-related toxicities.
13. Prior unanticipated severe reaction to fluoropyrimidine therapy, or known sensitivity to 5-fluorouracil, leucovorin, irinotecan, or panitumumab.
14. Treatment for other carcinomas within the last three years, except cured non-melanoma skin and treated in-situ cervical cancer.
15. Concomitant use of strong CYP3A4 inducers are not permitted.
16. Participation in any investigational drug study within 4 weeks preceding enrollment.
17. Other serious uncontrolled medical conditions that the investigator feels might compromise study participation.
18. Incomplete recovery from major surgery within 4 weeks of enrollment.
19. Unwillingness to give written informed consent.
20. Unwillingness to participate or inability to comply with the protocol for the duration of the study.
21. Patients with HIV/AIDS and those severely immunocompromised will be excluded. However, no patients will be tested for HIV.

5. REGISTRATION PROCEDURES

Subsite patients will have eligibility verified and will be centrally registered at The Ohio State University by the OSU Subsite Coordinator. Subsites should call or email the OSU Subsite Coordinator to verify enrollment availability prior to consenting patients.

Following registration, patients should begin protocol treatment within 5 business days. Issues that may cause treatment delays should be discussed with the OSU Principal Investigator as soon as possible. If a patient does not receive protocol therapy following registration, the patient will be replaced. The OSU Subsite Coordinator must be notified immediately if a patient does not receive protocol therapy.

Only patients deemed eligible by the subsite research team should be sent for eligibility verification and registration by the OSU Subsite Coordinator.

To request patient registration, the documents below must be completed by the subsite research team and faxed or securely emailed to the OSU Subsite Coordinator. If secure email is the preferred method and the subsite does not have a confirmed secure email system, the OSU secure email system may be used. Contact the OSU Subsite Coordinator for more information.

Required documents for registration:

- Enrollment Form (Appendix 5)
- Signed Eligibility Checklist (Appendix 6)
- Source documents verifying every inclusion & exclusion criteria
- Required screening items as listed in the Protocol Calendar. Screening tests must be

within the specified window.

- Emails and other signed forms used as source documentation

The OSU Subsite Coordinator will confirm receipt of the registration documents with the subsite contact listed on the Enrollment Form (Appendix 5). If confirmation is not received within 2 hours, it is strongly recommended that the subsite call the OSU Subsite Coordinator to confirm registration documents were received.

Registration requests will be processed as soon as possible and no later than 1 business day after receipt of the registration documents, pending there is no additional information needed to complete eligibility verification. Patients will be registered immediately upon determining they meet eligibility criteria.

The Subsite Coordinator will securely email the subsite contact listed on the Enrollment Form (Appendix 5) with the registration confirmation, and the patient's assigned study number.

6. DETAILED STUDY ASSESSMENTS

6.1. Informed Consent

The investigator must ensure written informed consent from each individual participating in this study after adequate explanation of the aims, methods, objectives and potential hazards of the study **prior** to undergoing any study-specific procedures.

6.2. Screening Procedures

This study will be conducted in patients with metastatic/unresectable advanced colorectal cancer. Patients may have been treated in the adjuvant setting with prior chemotherapy, but in the metastatic setting, should not have received more than one line of previous chemotherapy or biologic therapy. The patient's tumor sample must be evaluated for *RAS* mutation status prior to enrollment and must be unmutated (wild-type). The patients will be included if upon pathologic confirmation of metastatic disease has been confirmed, radiographic assessment has been completed, and meet the above listed inclusion and exclusion criteria will be eligible. Patients will be evaluated by their treating physician, the study coordinator, and/or the protocol investigator prior to enrollment. The screening procedures will be performed within 28 days prior to the start of treatment. The patients should not have received and bevacizumab within 3 weeks of starting treatment on this study. Pregnancy determination will occur within 7 days prior to study entry.

6.3. Pre-Study Assessment

6.3.1 To be completed within 28 days prior to treatment:

- a. Baseline measurements of tumor size based on CT scans and other relevant scanning to be used to document tumor status (includes full assessment of all known metastatic disease)
- b. Informed consent
- c. Adverse events

- d. ECG
- e. Malignant Disease/Treatment History
- f. Demographic Data
- g. General Physical Exam
- h. Hematology
- i. Concomitant Diseases & Treatments

6.3.2 To be completed within seven days prior to treatment:

- a. Medical History
- b. Physical examination, and weight
- c. Performance status
- d. CEA serum level
- e. Complete blood count with leukocyte differential
- f. Platelet count
- g. Serum chemistries, glucose and electrolytes (calcium, inorganic phosphate), liver function tests, uric acid
- h. Urinalysis,
- i. PT (or INR), PTT.
- j. Medication history
- k. Pregnancy test (women of childbearing potential) on serum B-HCG

6.3.3 To be completed prior to enrollment in the study:

- a. RAS mutation testing

6.4. Assessment during Treatment

The following will be obtained at regular intervals during treatment:

- a. History and physical examination Day 1 of each cycle
- b. Vital signs and weight assessment will be obtained prior to day 1 and day 15, (within 2 days).
- c. Drug toxicity (Adverse Drug Events) will be assessed every two weeks (toxicities will be graded according to the NCI CTC version 4.0).
- d. Complete blood count and serum chemistries (electrolytes including magnesium, calcium, potassium, BUN, Creatinine, liver function tests) will be obtained within 48 hours prior to each treatment, days 1 and 15.
- e. CEA serum level every as a baseline and once every cycle.
- f. Imaging studies including but not limited to CT scans prior to treatment as a baseline and every 8 weeks (+/- 5 days).

6.4.1 On-Study Follow-Up Assessment

The following will be obtained at the end of the study

- a. Adverse events/toxicities
- b. Monitor for inflammatory or infectious sequela in patients with severe dermatologic toxicities.
- c. Performance status
- d. Weight

- e. Vital signs (blood pressure, pulse rate, respiratory rate, temperature)
- f. Physical examination
- g. Reevaluation of extent of tumor (same imaging method)

6.4.2 After Study Assessment.

After completion of the study, electrolytes including magnesium, calcium, potassium will be followed every two weeks for the duration of 8 weeks after completion of panitumumab therapy.

6.5. Schedule of Assessments and Procedures

	Screening/Baseline		Every Treatment Cycle ^a		End of Study Visit
Day of Cycle	Within 28 days prior to first dose	Within 7 days prior to first dose	1	15	
5-FU bolus then cont infusion (over 46 hours)			X	X	
Irinotecan			X	X	
Panitumumab*			X	X	
Informed Consent ^b	X				
Medical History		X			
Malignant Disease / Treatment History	X				
Demographic Data	X				
General Physical Examination ^e	X	X	X		X
Vital Signs, Height, Weight, ECOG Performance Status		X	X	X	X
CBC ^g	X	X	X ^f	X	X
Complete Metabolic Panel Creatinine Clearance #		X	X ^f		X
Magnesium, potassium ^g		X	X ^f	X	X
CEA		X	X ^f		X
Urinalysis		X	— as clinically indicated —		
PT (or INR) & PTT		X	— as clinically indicated —		
Serum B-HCG ^c		X	— as clinically indicated —		
Tumor measurements (CT Scan)	X		Tumor measurements to be done after every 8 weeks of therapy		X
ECG	X		— as clinically indicated —		X

Adverse Events	X		— recorded throughout study	X
Concomitant Diseases & Treatment	X		— any changes noted throughout study —	X
KRAS and NRAS mutation testing ^d	X			

#Creatinine clearance is only required for baseline labs

*Minocycline will be given prophylactically for all patients starting the day prior to starting panitumumab and continue throughout the treatment duration (Please refer to section 6.2 for more details)

- a Each cycle is 28 Days, then repeated. Clinic visits can be performed +/- 2 days of treatment.
- b Informed consent must be obtained prior to any study-specific procedure
- c Only in women of childbearing potential
- d Archived tumor samples may be sent when they can be obtained at any time after screening process is started. May already completed prior to 21 days of enrollment.
- e Day 1 Cycle 1 is a chemotherapy only appointment. Clinic visit with physician is permitted but not mandatory
- f Day 1 Cycle 1 does not require labs to be repeated
- g Only CBC, magnesium and potassium to be obtained on day 15
- h MRI permitted with approval from PI
- i Survival data will be collected after the 8 week study assessment follow-up via chart review and/or phone follow-up every 3 months.

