6.7. Safety Parameters

6.7.1. Laboratory Tests

Laboratory tests during treatment will be performed according to the Schedule of Assessments and Procedures.

The following laboratory tests during treatment will be performed according to the Schedule of Assessments and Procedures.

- Complete Blood Count including differential, WBC, RBC, hemoglobin, hematocrit, platelet count
- Total bilirubin, AST/ALT, alkaline phosphatase, albumin, and total protein
- Conjugated (direct) bilirubin in the case of abnormal total bilirubin
- Serum creatinine and uric acid
- Glucose
- Electrolytes (sodium, potassium, magnesium)

- Serum calcium and inorganic phosphate
- Urinalysis (pH, protein, glucose and blood) (as clinically indicated)

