7.4. Dose Adjustment for 5FU and Irinotecan Toxicities

A cycle is 4 weeks – with treatment on days 1 and 15. We do not make up day #15 treatments if a patient should require adjustment or omission based on outlined criteria below.

- This study will take into consideration previous toxicities experienced with FOLFIRI prior to enrollment. The initial dose of FOLFIRI will be determined by the investigator at time of trial initiation. Prior to enrollment, if the patient experienced significant toxicity with FOLFIRI and dose adjustments were required, these dose adjustments will continue upon initiation of this trial.
- For toxicities which are considered by the investigator unlikely to develop into serious or life-threatening events (e.g. alopecia, altered taste etc.), treatment will be continued at the same dose without reduction or interruption. In addition, no dose reductions or interruptions will be required for anemia as it can be satisfactorily managed by transfusions.
- For any event that is apparent at baseline, the dose modifications will apply according to the corresponding shift in toxicity grade, if the investigator feels it is appropriate. (e.g. if a patient has grade 1 asthenia at baseline which increases to grade 2 during treatment, this will be considered as a shift of 1 grade and treated as a grade 1 toxicity for dose modification purposes).
- If on the first day of chemotherapy treatment, the granulocyte count (ANC) is < 1,500 or the platelet count is < 75,000, treatment will be held for up to three weeks until ANC is ≥ 1200 and platelet count is ≥ 75,000. CBC should be obtained at least weekly when treatment is held. Chemotherapy doses will not be reduced based on nadir counts except in febrile neutropenia as defined below.
- If the dose is modified to manage an adverse event, it is recommended that the patient be seen by the investigator prior to re-starting study drug.
- If a rest period is extended due to toxicity, the "complete" cycle should be given afterwards with chemotherapy and panitumumab. If toxicity requires a dosing delay/interruption of both 5-FU and irinotecan of more than six weeks or at the

discretion of the investigator, the patient will be withdrawn from the study for toxicity reasons.

Table 1: Dose modifications during a course of therapy (day #15 of each cycle).

- Dose adjustments for hematological toxicity during a course of therapy are based on the blood counts obtained in preparation for that day of treatment.

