- All dose adjustments are relative to dose given at on day #1 of that cycle.

FOLFIRI Regimen Dose Modification Guideline^a

Dose Modifications for the Next Cycle Based on the Worst Toxicity Observed ^{b,f}		
Toxicity Grade ^b (CTCAE v4.0)	5-FU bolus and continuous infusion	Irinotecan
Neutropenia, Thrombocytopenia, and Leukopenia (since prior treatment)		
0 or 1	Maintain dose level	Maintain dose level
2	Discontinue 5-FU bolus	Maintain dose level
3	Discontinue 5-FU bolus and ↓ 1 dose level continuous infusion	↓ 1 dose level
4	Discontinue 5-FU bolus and ↓ 2 dose levels continuous infusion	↓ 2 dose levels
Neutropenic fever or infection ^c	Discontinue 5-FU bolus and ↓ 2 dose levels continuous infusion	↓ 2 dose levels
Diarrhea ^d (since prior treatment)		
0 or 1	Maintain dose level	Maintain dose level
2	Discontinue 5-FU bolus and ↓ 1 dose level continuous infusion	Maintain dose level
3	Discontinue 5-FU bolus and ↓ 1 dose level continuous infusion	↓ 1 dose level
4	Discontinue 5-FU bolus and ↓ 2 dose levels continuous infusion	↓ 2 dose levels
Mucositis/Stomatitis (since prior treatment)		
0, 1 or 2	Maintain dose level	Maintain dose level
3	Discontinue 5-FU bolus	Maintain dose level
4	Discontinue 5-FU bolus and ↓ 1 dose level continuous infusion	Maintain dose level
Vomiting (since prior treatment)		
0, 1 or 2	Maintain dose level	Maintain dose level
3	Maintain dose level	↓ 1 dose level
4	Discontinue 5-FU bolus ↓ 1 dose level continuous infusion	↓ 1 dose level

Palmar-plantar erythrodysesthesia			
0, 1 or 2	Maintain dose level	Maintain dose level	
3	Discontinue 5-FU bolus ↓ 1 dose level continuous infusion	Maintain dose level	
Other nonhematologic toxicities (except alopecia and skin-related toxicities) ^e			
0, 1 or 2	Maintain dose level	Maintain dose level	
3	Discontinue 5-FU bolus ↓ 1 dose level continuous infusion	↓ 1 dose level	
4	Discontinue 5-FU bolus ↓ 2 dose levels continuous infusion	↓ 2 dose levels	

^a There will be no leucovorin dose reduction. If 5-FU bolus dropped, leucovorin will be discontinued as well.

^b NCI CTCAE(Version 4.0) (Appendix E)

^c Absolute Neutrophil Count <1000/mm³ and Temperature ≥ 38.5°C

^d Despite maximum supportive care

^e Bilirubin grade 3 and grade 4 hold dose: once the bilirubin level has resolved to ≤ grade 1 a dose reduction for 5-FU and irinotecan is required.

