Interruption of Panitumumab Infusion

Subjects who experience any serious infusion reaction during panitumumab administration will have the infusion stopped. Continuation of dosing will be based on the severity and resolution of the event and will be at the discretion of the investigator. Suspected infusion reactions should be reported as an adverse event. All subjects who experience such an event will be followed for safety.

Toxicity Assessment

Toxicities will be recorded as adverse events on the Adverse Event case report form and must be graded using The National Cancer Institute's Common Toxicity Criteria (CTCAE) version 4.0 (Appendix 4), with the exception of skin- or nail-related toxicities, which must be graded using CTCAE version 3.0 with modifications (see Appendix 4a).

Panitumumab Dosage Adjustments

For subjects who experience toxicities while on study, one or more doses of panitumumab may need to be withheld, reduced, or delayed (administered at > 14 day intervals). On resolution of toxicity, a limited number of attempts to re-escalate reduced panitumumab doses will be allowed (outlined in Figure 4). Dose escalations above 6 mg/kg starting dose are not allowed. Panitumumab dose reductions are listed in Table 3.

Table 3. Panitumumab Dose Reductions

	Starting Dose	1 st Dose Reduction	2 nd Dose Reduction
Percentage (%)	100	80	50
mg/kg	6	4.8	3.0

Criteria for Withholding a Dose of Panitumumab

Skin- or nail-related toxicities:

- Symptomatic skin- or nail-related toxicity requiring narcotics, systemic steroids, or felt to be intolerable by the subject
- Skin or nail infection requiring IV antibiotic or IV antifungal treatment
- Need for surgical debridement
- Any skin- or nail-related serious adverse event

Non-skin- or nail-related toxicities:

Any grade 3 or 4 toxicity with the following exceptions:

- Panitumumab will only be withheld for symptomatic hypomagnesemia and/or hypocalcemia that persists despite aggressive magnesium and/or calcium replacement
- Panitumumab will only be withheld for grade 3 or 4 nausea, diarrhea, or vomiting that persists despite maximum supportive care (see Section 6.6 and 6.7.1 for diarrhea management guidelines)
- Panitumumab will only be withheld for grade ≥ 3 anemia or grade 4 thrombocytopenia that can not be managed by transfusion(s) or cytokine therapy

Criteria for Re-treatment with Panitumumab

Skin- or nail-related toxicities:

- Panitumumab administration may recommence once:

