- The adverse event has improved to \leq Grade 2 or returned to baseline, and;
- The subject has recovered to the point where symptomatic skin- or nail-related toxicity is felt to be tolerable; and,
- Systemic steroids are no longer required, and
- IV antibiotic or IV antifungal treatment is no longer required

Non-skin- or nail-related toxicities:

- Panitumumab administration may recommence once the adverse event has improved to \leq Grade 1 or returned to baseline.

Dose Modification Schedule

- Subjects should be assessed for toxicity before each dose. Dose modification should be performed according to the schedule described below and outlined in Figure 1.

- Subjects who develop a toxicity that does not meet the criteria for withholding a dose of panitumumab (Section 6.5) should continue to receive panitumumab and their symptoms should be treated.
- Panitumumab-related toxicity will be considered resolved if it improves to a degree that allows for re-treatment with panitumumab (Section 6.5).
- For subjects who experience a toxicity that meets the criteria for withholding a dose of panitumumab:
 - Subjects receiving either 100% or 80% of the starting dose of panitumumab are allowed to have up to 2 subsequent doses withheld for toxicity. The second dose should only be withheld if the toxicity has not resolved by the time that the subsequent dose is due. Subjects treated at the 100% dose level whose toxicity resolves after 1 dose of panitumumab is withheld should be re-started at the 100% dose level (recommended but not required, reduction to the 80% dose is allowed as an alternative to re-challenge with the 100% dose).
 - If toxicity recurs, subjects treated at the 100% dose or 80% dose should be re-started at the 80% dose or 50% dose, respectively, when the toxicity resolves after withholding 1 or 2 doses of panitumumab.
 - Subjects treated at the 100% dose level whose toxicity resolves only after 2 subsequent doses of panitumumab are withheld should be re-started at the 80% dose level.
 - Subjects treated at the 80% dose level whose toxicity resolves after withholding 1 or 2 doses of panitumumab should be re-started at the 50% dose level.
 - Subjects who experience toxicity at the 50% dose level will not be re-treated with panitumumab.

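### Sections 6.4 and 6.5 disagree on day-15 laboratory tests; if the schedule is followed, every second dose is given without a planned bilirubin, AST/ALT or creatinine

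*Combined protocol and SAP*

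**What the plan says.** - **Section 6.4, item d.** Blood counts and serum chemistries (naming magnesium, calcium, potassium, BUN, creatinine and liver function tests) "will be obtained within 48 hours prior to each treatment, days 1 and 15".
- **Section 6.5, schedule.** The metabolic panel is marked within 7 days before the first dose, on day 1 of each cycle and at the end of study. The day-15 cell is empty, while the CBC and the magnesium/potassium rows are marked on day 15. Footnote g puts the same thing in words: "Only CBC, magnesium and potassium to be obtained on day 15". Footnote f adds: "Day 1 Cycle 1 does not require labs to be repeated".
- **Section 6.7.1.** Bilirubin, AST/ALT and creatinine are on the safety list, but their timing is handed to the schedule: "Laboratory tests during treatment will be performed according to the Schedule of Assessments and Procedures".
- **Section 7.2.** All study drugs are given on days 1 and 15 of a 28-day cycle.
- **Section 7.4.** The caption of Table 1 reads "Dose modifications during a course of therapy (day #15 of each cycle"). Footnote e of the modification table begins: "Bilirubin grade 3 and grade 4 hold dose: once the bilirubin level has resolved".
- **Section 7.5.** Outside skin and nail toxicity, panitumumab is withheld for "Any grade 3 or 4 toxicity with the following exceptions". On timing: "Subjects should be assessed for toxicity before each dose".

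**The concern.** A site cannot satisfy both 6.4(d) and footnote g. If it follows the schedule, no bilirubin, AST/ALT or creatinine is planned before the day-15 treatment, yet two dose rules depend on such values. One is the hold for grade 3-4 bilirubin. The other is the withholding of panitumumab for grade 3-4 non-skin toxicity, whose listed exceptions do not include bilirubin, transaminases or creatinine. A new abnormality without symptoms would trigger neither rule until the next cycle.

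The protocol gives its own reasons to watch these values. With liver metastases, patients may enter with AST/ALT just under 5 times the upper limit of normal, and creatinine clearance may be as low as 30 ml/min (4.1). Section 7.9.2 notes occasional creatinine abnormalities with irinotecan. Toxicity frequency and severity is also a secondary objective (2.2). If the two participating institutions follow different sections, laboratory toxicity will be detected unevenly between them.

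**Working it through.** The plan states no figure to reproduce. The check compares the two rules and counts what each provides.

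**Inputs**
- Doses on days 1 and 15, cycle of 28 days (6.5 footnote a, 7.2).
- Baseline panel 0 to 7 days before the first dose (6.3.2, 6.5).
- Cycle 1 day 1 laboratory tests waived (6.5 footnote f).
- Pre-dose window of 48 hours (6.4(d)), applied to both versions.
- Six cycles as the illustration, being the point at which 7.3 allows a switch to panitumumab alone.
- Assumptions: the metabolic panel row is where bilirubin, AST/ALT and creatinine sit, since no other row could hold them; doses fall on their nominal days, so the ±2-day visit window is not added.

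**Doses with no planned panel since the preceding dose**
- Schedule: every day-15 dose, so 1 of 2 per cycle; over six cycles 6 × 1 = 6 of 6 × 2 = 12.
- 6.4(d): 0 of 12, with the baseline panel serving for the first dose.

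**Baseline panel to first on-treatment panel**

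With the first dose on day 1, the baseline panel falls between day 1 − 7 = −6 and day 1.
- Schedule: next panel 0 to 2 days before day 29. Shortest gap (29 − 2) − 1 = 26 days; longest 29 − (−6) = 35 days. Two doses fall in between.
- 6.4(d) with the footnote f waiver: next panel 0 to 2 days before day 15. Shortest gap (15 − 2) − 1 = 12 days; longest 15 − (−6) = 21 days. One dose falls in between.

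**On-treatment pre-dose panels over six cycles**
- Schedule: day 1 of cycles 2 to 6, so 6 − 1 = 5.
- 6.4(d): all 12 doses less the waived first one, so 12 − 1 = 11.

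| | Schedule (6.5) | 6.4(d) |
|---|---|---|
| Doses without a panel since the preceding dose | 6 of 12 | 0 of 12 |
| Baseline to first on-treatment panel | 26-35 days, two doses | 12-21 days, one dose |
| Later interval between panels | about 28 days | about 14 days |
| On-treatment pre-dose panels | 5 | 11 |

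**The case against.** The strongest reply is that the documents lean towards the schedule and that the lighter day-15 panel may be deliberate. Section 6.7.1 defers to the schedule. So do 3.1 and the electrolyte paragraph in 7.5, through references to a section 5.5 that appears to be an old number for 6.5. Under the Table 1 caption, same-day adjustment is tied explicitly only to blood counts, which the schedule does provide on day 15. The table holding the non-hematologic rows is headed as applying to the next cycle, when a panel is planned. On this reading, 6.4(d) is a leftover sentence, and deleting its day-15 chemistry would also end the contradiction.

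Much of this is fair, and it weakens the Table 1 caption as evidence. Two points remain. The bilirubin hold names no day, and panitumumab toxicity is to be judged before each dose, so both rules still need chemistry on day 15. And the more the text favors the schedule, the more likely it is that sites omit the panel.

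It is also true that the exposure is narrow. Section 9.1 requires unexplained abnormal values to be repeated, and 6.4(c) has toxicity assessed every two weeks. Acute renal failure, as described in 1.2.1.5, follows severe diarrhea and dehydration, which would be noticed clinically. Missing calcium is minor: withholding requires symptomatic, persistent hypocalcemia, and 7.5 already asks for calcium to be assessed when magnesium is low. These points limit the risk to new, silent abnormalities but do not remove it.

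**Conclusion.** The concern holds. The conflict is in the current text, and no other section restores a day-15 chemistry panel. The empty table cell is not an extraction fault, because footnote g says the same in words.

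If the schedule governs, half of all doses lack a planned panel since the preceding dose, and the first check of liver and renal chemistry on treatment comes only before the third dose. The counts rest on nominal dosing days and on the reading of the metabolic panel row given above. They count panels, not missed events: the documents give no rate for silent grade 3-4 changes, so the clinical consequence cannot be sized. Sample size and the analysis of progression-free survival are untouched. The correction should be made, because stated dose-hold rules otherwise lack the data they need.

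**What to change.** In the 6.5 schedule, mark the metabolic panel (without creatinine clearance, which is a baseline test only) for day 15. Reword footnote g to agree with 6.4(d), for example: *CBC, metabolic panel, magnesium and potassium to be obtained on day 15, within 48 hours before treatment.*

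The change is one table cell and one footnote. It costs one extra chemistry panel per cycle, on blood already drawn that day and already required by 6.4(d). If the lighter panel was intended, 6.4(d) has to be corrected instead, and 7.4 and 7.5 should then say how the bilirubin hold and the panitumumab rule are applied on day 15 without these values. Adding the panel is the safer choice.
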